10.5.3. Secondary PK Analysis

Secondary efficacy analyses 2 and 5 will be based on the secondary PK population.

Secondary efficacy analyses 1, 3, and 4 will be based on the primary PK population, since timepoints post-Visit 6 are not included in these analyses.

The secondary PK endpoints will be analyzed as follow:

- 1) the assessment AUC_{0-7d} for BPL HRIG and vaccine versus comparator HRIG and vaccine using a non-inferiority margin of 20%.
- 2) the geometric mean titers (GMTs) for RVNA titer up to peak serum level after administration of BPL HRIG and vaccine or comparator HRIG and vaccine will be assessed using a mixed model repeated measure [MMRM] analysis.
- 3) the proportion of subjects reaching anti-rabies antibody titer of ≥ 0.5 IU/mL at Visits 3-6 after administration of BPL HRIG and vaccine versus comparator HRIG and vaccine will be assessed using a generalized estimated equation [GEE] for a repeated measure analysis.
- 4) the proportion of subjects reaching anti-rabies antibody titer of \geq the lower limit of quantification (LLOQ) of the assay at Visit 3-6 after administration of BPL HRIG and

vaccine versus comparator HRIG and vaccine will be assessed using a generalized estimating equation [GEE] for a repeated measure analysis.

- 5) the GMTs for anti-rabies antibody titer at Visits 6-9 will be compared between treatment groups. Descriptive statistics and visual inspections will be reported as appropriate. No formal hypothesis testing will be performed.

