2. STUDY OBJECTIVES

The objectives of this study are:

1. To demonstrate non-inferiority of BPL HRIG compared to an FDA-licensed HRIG product, in terms of the proportion of subjects achieving anti-rabies antibody titer of ≥ 0.5 IU/mL at Day 14 following treatment with HRIG in conjunction with active rabies vaccine.

2. To compare the PK of BPL HRIG in conjunction with active rabies vaccine, with FDA-licensed HRIG product in conjunction with active rabies vaccine.
3. To assess whether BPL HRIG interferes with the development of the host-immune response when given simultaneously with active rabies vaccine, relative to an FDA-licensed HRIG product.
4. To evaluate the safety and tolerability of BPL HRIG in comparison with FDA-licensed HRIG product.

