6. STUDY ENDPOINTS

The PRIMARY efficacy endpoint is to demonstrate non-inferiority of BPL HRIG compared to a FDA-licensed HRIG product, in terms of:

- the proportion of subjects with anti-rabies antibody titer of ≥ 0.5 IU/mL on day 14 after administration of BPL HRIG and vaccine versus comparator HRIG and vaccine, using a non-inferiority margin of 10%.

The SECONDARY efficacy endpoints are as follows:

1. Assessment of AUC_{0-7days} for BPL HRIG+vaccine vs. comparator HRIG+vaccine using a non-inferiority margin of 20%.
2. Comparison of the geometric mean titers (GMTs) for anti-rabies antibody titer at Days 3, 5, 7, 14, and 28 after administration of BPL HRIG and vaccine versus comparator HRIG and vaccine.
3. The proportion of subjects reaching anti-rabies antibody titer of ≥ 0.5 IU/mL at Days 3, 5, 7, 14, 28, 49, and 140 after administration of BPL HRIG and vaccine versus comparator HRIG and vaccine.
4. The proportion of subjects reaching anti-rabies antibody titer of \geq the lower limit of quantitation of the assay at Days 3, 5, 7, 14, 28, 49 and 140 after administration of BPL HRIG and vaccine versus comparator HRIG and vaccine.
5. Comparison of the geometric mean titers (GMTs) for anti-rabies antibody titer at Days 14, 28, 49, and 140 after administration of BPL HRIG and vaccine versus comparator HRIG and vaccine to assess the inhibitory effects of BPL HRIG on active immunization relative to that of the comparator HRIG.

An EXPLORATORY efficacy endpoint is as follows:

The following PK parameters for anti-rabies antibody concentrations for both treatment groups:

- C_{\max} [IU/mL]
- T_{\max} [day]
- area under the concentration vs time curve to the last measurable concentration (AUC_{0-t}) [day*IU/mL]
- apparent terminal rate constant (λ_z) [day^{-1}]
- $AUC_{0-7 \text{ days}}$ [day*IU/mL]
- area under the concentration vs time curve to infinity ($AUC_{0-\infty}$), if appropriate
- $C_{\max}/AUC_{0-\infty}$ [or C_{\max}/AUC_{0-t} if $AUC_{0-\infty}$ cannot be estimated]
- half-life ($t_{1/2}$), if appropriate

The following will be used to assess the SAFETY of BPL HRIG and vaccine, versus comparator HRIG and vaccine:

- Adverse events
- Injection site observations
- Viral serology
- Serum biochemistry, hematology and urinalysis
- Markers of hemolysis
- Physical examination
- Vital signs

The following additional tests will additionally be performed:

- pregnancy tests (for females of childbearing potential).

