The second secondary analyses will be performed using an appropriate mixed model repeated measures [MMRM] analysis to assess for differences of the slope and the change in GMT of the titers at the days described below. The correlation structure involves multiple pieces, including measurement errors, random variation, and inter-individual variability. For the longitudinal data analysis, an unstructured correlation matrix for within-subject error will be assumed. Other correlation structures, including compound symmetry, will be examined as needed. The validity of this model will be assessed via standard modeling diagnostics and goodness-of-fit measures. Comparisons of geometric mean titers [GMTs] between the treatment group at each timepoint and across all timepoints will be reported. The final output will include one row indicating the mean change [95% confidence intervals] in titer across all PK assessments from Visit 2 [baseline] through Visit 7 by treatment group and one row for every specific timepoint thereafter. Additionally, the difference in the means [or the ratio of the GMT] between treatment groups, the corresponding 95% confidence intervals, associated chi-square test statistic, and p-value will be reported. A p-value of <0.05 will signal a statistically significant difference in titers. See table below for example output:

Parameter	Treatment Group Ns			Mean Change From Baseline (95% Confidence Intervals)		BPL HRIG + Vaccine versus Comparator HRIG + Vaccine		
	N _{BPL}	N _{CP}	N _T	BPL HRIG + Vaccine	Comparator HRIG + Vaccine	Difference in Means (95% CI)	Chi-Square	P-Value
Through Day 28	x	x	x	x.xx (x.xx, x.xx)	x.xx (x.xx, x.xx)	x.xx (x.xx, x.xx)	x.xx	0.xxx
Day 3	x	x	x	x.xx (x.xx, x.xx)	x.xx (x.xx, x.xx)	x.xx (x.xx, x.xx)	x.xx	0.xxx
Day 5	x	x	x	x.xx (x.xx, x.xx)	x.xx (x.xx, x.xx)	x.xx (x.xx, x.xx)	x.xx	0.xxx
Day 7	x	x	x	x.xx (x.xx, x.xx)	x.xx (x.xx, x.xx)	x.xx (x.xx, x.xx)	x.xx	0.xxx
Day 14	x	x	x	x.xx (x.xx, x.xx)	x.xx (x.xx, x.xx)	x.xx (x.xx, x.xx)	x.xx	0.xxx
Day 28	x	x	x	x.xx (x.xx, x.xx)	x.xx (x.xx, x.xx)	x.xx (x.xx, x.xx)	x.xx	0.xxx

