5. The geometric mean titers (GMTs) for anti-rabies antibody titer at Visit 6-9 will be compared between treatment groups. Descriptive statistics and visual inspections will be reported as appropriate. No formal hypotheses testing will be performed.

g. EXPLORATORY PK ANALYSES

The following PK parameters for anti-rabies antibody concentrations will be summarized for both treatment groups:

- C_{\max} [IU/mL]
- T_{\max} [day]
- area under the concentration vs time curve to the last measurable concentration (AUC_{0-t}) [day*IU/mL]
- apparent terminal rate constant (λ_z) [day⁻¹]
- AUC_{0-7d} [day*IU/mL]
- area under the concentration vs time curve to infinity ($AUC_{0-\infty}$), if appropriate

- $C_{\max}/AUC_{0-\infty}$ [or C_{\max}/AUC_{0-t} if $AUC_{0-\infty}$ cannot be estimated]
- half-life ($t_{1/2}$), if appropriate

Non-compartmental PK methods will be utilized to calculate the subject level PK parameters. C_{\max} , AUC_{0-t} , AUC_{0-7d} , $AUC_{0-\infty}$, apparent terminal rate constant (λ_z), and $t_{1/2}$ will be dose normalized by dividing the raw PK parameters by the actual dose the subject received. A t-test will compare the PK and dose-normalized PK parameters between treatment groups. Log-transformations will be performed as necessary during statistical analysis when appropriate.

h. ADVERSE EVENT REPORTING

Adverse events (AEs) will be reported by the MedDRA system organ class and preferred term. Only treatment emergent AEs (i.e. beginning after dosing with BPL HRIG / vaccine or comparator HRIG / vaccine) will be included in the summary tables. All AEs will be included in the data listings.

Treatment-related AEs will be defined as events recorded as having a possible, probable or very likely/certain causality to treatment. AEs leading to withdrawal will be defined as events where the subject's participation in the study was discontinued as a result of the AE.

AEs will be summarized descriptively for all subjects and by treatment group. The denominator used for the calculation of percentages will be the number of subjects in the safety population per treatment group. For all AE summaries described below, counting will be performed by subject and event. For counts by subject, subjects experiencing the same event more than once will have that event counted only once within each system organ class and once within each preferred term.

The following summaries of treatment-emergent AEs will be provided:

SUMMARY OF AEs

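### Endpoint 5, the endpoint written for Objective 3, has no pre-specified between-arm GMT ratio with confidence interval at Days 49 and 140

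*SAP*

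**What the plan says.** Objective 3 (SAP 2; same in Protocol 3) is "To assess whether BPL HRIG interferes with the development of the host-immune response when given simultaneously with active rabies vaccine", relative to the licensed comparator. Secondary endpoint 5 (SAP 6, Protocol 8.1.2) takes the GMTs at Days 14, 28, 49 and 140 and states its purpose as "to assess the inhibitory effects of BPL HRIG on active immunization relative to that of the comparator HRIG". Protocol 2.9 also names these four days as the way attenuation will be studied.

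For the analysis, SAP 8.f item 5 says the GMTs "at Visit 6-9 will be compared between treatment groups". It continues: "Descriptive statistics and visual inspections will be reported as appropriate". It closes: "No formal hypotheses testing will be performed". Protocol 10.5.3 item 5 agrees: "No formal hypothesis testing will be performed". Neither document names an effect measure, an interval or a criterion for interference.

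Two other planned analyses bear on the objective. The endpoint 2 mixed model (SAP 8.f) reports a between-arm difference or GMT ratio with 95% CI, chi-square and p-value, and its example table has rows for Days 14 and 28. Separately, Protocol 2.9 says any attenuation seen will be described through the PK parameters, which SAP 8.g compares between arms by t-test as an exploratory analysis.

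**The concern.** Endpoint 5 is by its own wording a comparison of the two arms, but no measure of that comparison is specified. Summaries by arm and plots show whether the curves look alike. They do not say how large an attenuation the data exclude, and that is the useful answer to Objective 3.

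The gap falls on the two later visits. Early titers mix injected antibody with the subject's own response, so a weaker response to vaccine can be partly hidden. Later titers are less affected. The plan therefore provides interval estimates at Days 14 and 28, where passive antibody confounds more, and none between arms at Days 49 and 140, where it confounds less. Protocol 2.3 and 2.9 treat interference as a known effect of HRIG at a higher dose, so the objective is not a formality.

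**Working it through.** **1. Which analysis covers which visit**

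| Analysis | Day 14 | Day 28 | Day 49 | Day 140 | Between-arm output |
|---|---|---|---|---|---|
| Endpoint 2 MMRM (SAP 8.f) | yes | yes, unless the peak comes earlier | no | no | difference or GMT ratio, 95% CI, p-value |
| Endpoints 3 and 4 GEE (SAP 8.f) | proportions only | no | no | no | not a GMT contrast |
| Endpoint 5 (SAP 8.f) | yes | yes | yes | yes | none named |
| Exploratory PK (SAP 8.g) | profile summaries | same | same | same | t-test; no interval named; not by visit |

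The MMRM output runs from Visit 2 through Visit 7. Its text promises a row for each later time point, but this refers to the rows under the overall line, and the example table ends at Day 28. Endpoints 2 and 5 use the same secondary PK population.

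**2. Passive antibody left at each visit**

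Input: half-life of 3 to 4 weeks, i.e. 21 to 28 days (Protocol 2.4 and 2.9). Fraction left = 0.5^(day / half-life), counted from Day 0 and ignoring absorption.

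- Day 14: 0.5 to 0.67 half-lives, 71% to 63% left.
- Day 28: 1 to 1.33 half-lives, 50% to 40% left.
- Day 49: 1.75 to 2.33 half-lives, 30% to 20% left.
- Day 140: 140/28 = 5 to 140/21 = 6.7 half-lives, 3.1% to 1.0% left.

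Absorption is delayed, so these are approximate. Counting instead from the Day 13 passive peak cited in Protocol 2.3, Day 140 is 127/28 = 4.5 to 127/21 = 6.0 half-lives, with 4.3% to 1.5% of the peak left. The conclusion for Day 140 does not change. Day 49 is an intermediate case, but it is the sampling day nearest the Day 40 peak that Protocol 2.3 cites for HRIG with vaccine.

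**3. The plan's own sample size**

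Neither document states a size or precision for endpoint 5. The only figure available is the primary endpoint's 73 per group (Protocol 10.9). It reproduces by the Farrington-Manning formula with success 98% in both arms, margin 0.10, one-sided 0.025 and power 85%. The restricted estimates under the null are 0.8895 and 0.9895.

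- s0 = sqrt(0.8895 × 0.1105 + 0.9895 × 0.0105) = 0.3296
- s1 = sqrt(2 × 0.98 × 0.02) = 0.1980
- n = ((1.960 × 0.3296 + 1.036 × 0.1980) / 0.10)^2 = 72.4, rounded up to 73

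**4. Precision of a GMT ratio at that size**

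The documents give no SD for log titer; 0.3 to 0.6 on the log10 scale is an assumption. The 95% CI is the ratio multiplied or divided by 10^(t × SD × sqrt(2/n)). For n = 73, t on 144 df is 1.977 and sqrt(2/73) = 0.1655, so SD 0.3 gives 10^(1.977 × 0.3 × 0.1655) = 10^0.098 = 1.25.

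| Assumed log10 SD | 73 per arm | 60 per arm |
|---|---|---|
| 0.3 | 1.25 | 1.28 |
| 0.4 | 1.35 | 1.40 |
| 0.5 | 1.46 | 1.52 |
| 0.6 | 1.57 | 1.65 |

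The secondary PK population requires all five vaccine doses and all PK samples, so it may be smaller than 73 per arm. The 60 column is an illustration, not a figure from the plan.

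**The case against.** The best defence is that Objective 3 does not rest on plots alone. Days 14 and 28, half of endpoint 5, get a between-arm estimate with interval through endpoint 2 in the same population. AUC to the last measurable concentration draws on the late samples and is compared by t-test. No success criterion depends on endpoint 5, titers are summarised by arm at every time point, and a promise to compare does not rule out a ratio. All of this stands, and it limits the point to what is pre-specified at two visits.

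A reader might go further in four ways that the documents do not support.

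- **That the objective is answered by visual inspection only.** The endpoint 2 model and the PK comparison contradict this.
- **That Days 49 and 140 have no interval of any kind.** SAP 7 gives a 95% CI for the mean of continuous variables. SAP 8.a has a shorter list without it, so this is not certain, but in any case such an interval is for each arm, not for the contrast.
- **That the plan handles the same titers inconsistently.** SAP 8.f gives a reason for stopping the endpoint 2 model at the peak: the relation of titer to time changes there.
- **That the plan would read a non-significant p-value as absence of interference.** The SAP says only that a value below 0.05 will "signal a statistically significant difference in titers", and it reports the interval beside it.

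What the defence does not supply is an interval for late attenuation. AUC and Cmax combine passive and active antibody, the endpoint 2 model is not assigned to Objective 3, and its cut-off at the peak could remove Day 28.

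**Conclusion.** The point holds in a narrow form. For endpoint 5, no between-arm GMT ratio with CI is pre-specified at Days 49 and 140. Day 140 is the visit at which the titer best reflects active immunity, given the stated half-life.

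This is a low-cost improvement rather than a defect that threatens the trial. The primary conclusion is unaffected, and the data needed are already collected. The gain is that the report could state how much late attenuation has been excluded. At 73 per arm, a 95% CI of about 1.25-fold to 1.57-fold either side of the ratio is attainable. That range rests on the assumed log10 SD of 0.3 to 0.6 and on the secondary PK population being close to the planned evaluable number. It shows that the estimate is feasible and does not measure any harm from the present text.

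**What to change.** In SAP 8.f item 5, and in Protocol 10.5.3 item 5 if it is amended, state that the BPL/comparator GMT ratio with 95% CI will be reported at Days 14, 28, 49 and 140. Label it as estimation, with no test and no margin; this is compatible with the existing statement that endpoint 5 is not formally tested. Keep the descriptive summaries and plots.

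Obtain the ratios in one of two ways, and name which:

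- per-visit contrasts of log titer between arms, back-transformed; or
- a separate log-titer MMRM through Visit 9 with visit as a categorical factor, so that the rise and fall of titer needs no slope assumption.

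Leave the pre-peak endpoint 2 model as it is.

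The cost is a small extra analysis. Days 49 and 140 are two new estimates, since Days 14 and 28 are already in the endpoint 2 output (Day 28 subject to its cut-off). No further samples are needed. The four intervals carry no multiplicity control and should be described as such.

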2.3. Development of HRIGs for Post-Exposure Prophylaxis

The usefulness of prophylactic rabies antibody in preventing rabies in humans when administered immediately after exposure was demonstrated in a group of persons bitten by a rabid wolf in Iran in 1954^{10,11}. A series of clinical studies helped determine the optimal conditions under which anti-rabies serum of equine origin and rabies vaccine could be used in humans^{12,13,14,15}. These studies showed that the anti-rabies serum could interfere with the active immunity induced by the vaccine, but could be minimized by booster doses of vaccine after the end of the usual dosage series.

Later development was the preparation of rabies immune globulin of human origin with adequate potency¹⁶. In carefully controlled clinical studies, this globulin was used in conjunction with rabies vaccine of duck-embryo origin^{16,17}. The recommended dose for HRIG of 20 IU/kg was established in clinical studies comparing the rabies IgG titer following various doses of HRIG and vaccine^{16,17,18}. A lower dose of 10 IU/kg was suboptimal for early protection and a higher dose of 40 IU/kg interfered with the development of active immunity conferred by the vaccine. At the dose of 20 IU/kg, anti-rabies antibody titers were detectable from Day 1 after the injection. Without injection of vaccine, passive antibody titers reached a peak of 30 IU/mL 13 days after Day 0 and declined with a half-life of approximately 3 weeks. However, when HRIG was administered with a course of rabies vaccine, rabies IgG levels continued to rise, peaking at Day 40 with a titer of 111 IU/mL¹⁷.

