In order to maintain blinding of treatment, the study will be blinded to the subject, investigator and site staff, to reduce bias in the identification and causality assessments of adverse events and laboratory abnormalities. An unblinded pharmacist or licensed medical professional will be responsible for preparation of the correct treatments according to the randomization code. In this study, actual (rather than nominal) HRIG potency will be used to calculate the volume of HRIG to be administered. Since there will be differences in the volume of the HRIGs the nurse administrator will also be unblinded. This modified blinding technique was successfully used in a completed study comparing PK and safety of two rabies vaccine formulations, both in conjunction with licensed HRIG²⁴.

A study duration of five times the half-life of the experimental treatment is usually considered adequate to identify safety issues relating to the product. The half-life of HRIG is 3-4 weeks¹⁹, therefore study duration of 15 to 20 weeks is considered appropriate both to obtain a full PK profile and for appropriate safety follow up. A duration of 140 days (20 weeks) has therefore been selected for this study.

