6.2. Randomized Treatment

Subjects will be randomized to receive one of two treatments described below.

Treatment A: BPL HRIG + rabies vaccine (RabAvert®).

A 20 IU/kg dose of BPL HRIG will be given on Day 0 via IM injection. The volume to be injected will be based upon the subject's weight on Day 0 and BPL HRIG actual potency (see pharmacy manual). A maximum of 5 mL will be administered to each lateral thigh and a maximum 2.0 mL to the deltoid muscle. The gluteal muscle will not be used for IM injection due to the increased variability of absorption from this injection site and the risk of injury to the sciatic nerve.

The total volume will be split between the injection sites as follows:

Table 5: Treatment A -total volume to be split between the injection sites

Injection number	Volume to be injected	Site of injection
1	up to 5 mL depending on bodyweight	left lateral thigh muscle
2	up to 5 mL depending on bodyweight	right lateral thigh muscle
3 (if required)	up to 2 mL depending on bodyweight	left deltoid muscle

A 1.0 ml dose of active vaccine (2.5 IU/ml) will be given IM on 5 occasions: on Days 0, 3, 7, 14, and 28. On day 0, the vaccine will be administered to the right deltoid muscle. The subsequent doses of vaccine on days 3, 7, 14, and 28 may be administered to the right or the left deltoid muscle.

The vaccine dose should never be administered into the same anatomical site as the HRIG.

Treatment B: FDA-approved comparator HRIG (HyperRAB[®] S/D) + rabies vaccine (RabAvert[®])

A 20 IU/kg dose of comparator HRIG will be given on Day 0 via IM injection. The volume to be injected will be based upon the subject's weight on Day 0 and BPL HRIG actual potency (see pharmacy manual). A maximum of 5 mL will be administered to each lateral thigh and a maximum 2.0 mL to the deltoid muscle. The gluteal muscle will not be used for IM injection due to the increased variability of absorption from this injection site and the risk of injury to the sciatic nerve.

The total volume will be split between the injection sites as follows:

Table 6: Treatment B -total volume to be split between the injection sites

Injection number	Volume to be injected	Site of injection
1	Up to 5 mL depending on body weight	left lateral thigh muscle
2	up to 5 mL depending on bodyweight	right lateral thigh muscle
3 (if required)	up to 2 mL depending on bodyweight	left deltoid muscle

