6.3. Product Administration

HRIG will be drawn into 2 or 3 (as appropriate according to the calculated volume) 5.0 mL syringes and injected to the lateral thighs and, if required, the left deltoid muscle.

Vaccine will be drawn into a 1.0 mL syringe and injected to the right deltoid muscle.

The selection of HRIG products to be administered (BPL HRIG or comparator HRIG) as per the randomized treatment, the calculation of the volume to be administered, and the drawing up of the appropriate volume into syringe(s), will be performed by the unblinded pharmacist/or licensed medical personnel. The selection of products to be administered, calculation of volume to be administered, and the volume in the syringe will be checked by the unblinded nurse administrator prior to administration to the subject.

For the BPL HRIG, comparator HRIG, the following details will be recorded:

- name of product
- lot number

-
- total dose required in IU, calculated from body weight (20 IU/kg)
 - total dose required in mL, calculated from the actual potency
 - for each specified injection site, actual dose administered in mL (this should not exceed 5.0 mL for each lateral thigh muscle and 2.0 mL for the left deltoid muscle)
 - date and time of injection on Day 0

See the pharmacy manual for additional information on calculations, potency and details to be recorded. Certificates of analysis for both products will be kept in BPL files.

For the rabies vaccine, the following details will be recorded:

- name of product
- lot number
- confirmation of actual dose given in mL (this should be 1.0 ml)
- date, time, and location of injection, on Days 0, 3, 7, 14, and 28

See the pharmacy manual for additional information on details to be recorded. For any given subject, every effort must be made to use the same lot of active rabies vaccine throughout the study.

For additional details on administration of BPL and comparator HRIG using actual potency versus nominal potency refer to [Appendix F](#) and the pharmacy manual.

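### Dose-normalising Cmax, the long AUCs, the terminal rate constant and the half-life by HRIG dose gives quotients with no clear meaning, and the unit of dose is not defined (exploratory analysis only)

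*SAP*

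**What the plan says.** SAP 8.g and Protocol 10.5.4 carry the same rule. Cmax, AUC0-t, AUC0-7d, AUC0-inf, the terminal rate constant and the half-life "will be dose normalized by dividing the raw PK parameters by the actual dose the subject received". Then "A t-test will compare the PK and dose-normalized PK parameters between treatment groups", with log-transformation where appropriate. Neither document gives a reason for normalising or says whether dose means total IU or IU/kg.

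Other relevant parts of the plan:

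- **HRIG dose.** It is 20 IU/kg (Protocol 6.2). Section 7.3.1 speaks of the dose in IU/kg. Section 6.3 has the total IU and the mL recorded, and the example in Appendix F works in total IU.
- **Vaccine dose.** It is the same for everyone: "A 1.0 ml dose of active vaccine (2.5 IU/ml) will be given IM on 5 occasions" (Protocol 6.2).
- **Population.** The exploratory analysis uses the secondary PK population, which requires the full HRIG dose (Protocol 10.4, SAP 7.b).
- **Background figures.** For HRIG without vaccine, Protocol 2.3 reports that "passive antibody titers reached a peak of 30 IU/mL 13 days after Day 0 and declined with a half-life of approximately 3 weeks". For HRIG with a vaccine course, "rabies IgG levels continued to rise, peaking at Day 40 with a titer of 111 IU/mL".
- **Purpose of AUC0-7d.** Protocol 2.9 chose it to look at HRIG before the vaccine response begins.

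**The concern.** Dividing an exposure measure by dose is meaningful when exposure is roughly proportional to that dose. The assay measures total neutralising antibody, passive and active together. If most of the peak and of the long AUCs comes from a fixed vaccine dose, dividing by HRIG dose does not give exposure per unit of HRIG. The rate constant and half-life are a separate case: under linear kinetics they do not change with dose at all, so no normalisation is called for.

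The undefined unit adds a second problem. In subjects who all received 20 IU/kg, total IU varies only because weight varies, whereas IU/kg hardly varies. One reading inserts body weight into the outcome and the other changes almost nothing.

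At stake is a set of p-values that would be reported under Objective 2 (comparison of PK) and that nobody could interpret.

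**Working it through.** The plan states no vaccine share of the titer, so there is no figure of its own to reproduce here. The shares below are derived.

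**1. Vaccine share of the peak.** Inputs from Protocol 2.3: passive peak 30 IU/mL at Day 13, half-life about 21 days, and 111 IU/mL at Day 40 with vaccine. Protocol 2.9 widens the half-life: "The half-life of HRIG is 3-4 weeks", so 21 to 28 days. The passive part is assumed to add to the active part.

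- Direct comparison, no decay: 1 - 30/111 = 73.0%.
- Half-life 21 days: passive titer at Day 40 = 30 x 0.5^(27/21) = 12.3 IU/mL; vaccine share = 1 - 12.3/111 = 88.9%.
- Half-life 28 days: 30 x 0.5^(27/28) = 15.4 IU/mL; vaccine share = 1 - 15.4/111 = 86.1%.

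These shares are for the peak only. For AUC0-140 a rough range needs further assumptions: straight-line rises (0 to 30 IU/mL by Day 13, then to 111 by Day 40), passive half-life 21 or 28 days, and a fall after the peak anywhere from a 21-day half-life to no decline.

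- Passive AUC = 0.5 x 30 x 13 + 30 x (h/ln 2) x (1 - 2^(-127/h)) = 1090 (h = 21) or 1355 (h = 28).
- Total AUC = 195 + 27 x (30 + 111)/2 + the part after Day 40 = 5337 (21-day half-life) to 13198 (no decline).
- Vaccine share: 1 - 1355/5337 = 75% to 1 - 1090/13198 = 92%.

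So AUC0-140 is also mostly vaccine, but 85% is not established for it.

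**2. What the divisor is.** With the full dose given, total IU = 20 x weight. Two subjects of 60 and 90 kg receive 1200 and 1800 IU. With the same Cmax, their quotients differ by a factor of 1800/1200 = 1.5. In IU/kg both divisors are 20 and the quotients are equal.

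**3. Cost in precision if the divisor is total IU.** The documents give no CVs. Assume a weight CV of 15% and a parameter that does not depend on weight at 20 IU/kg. The log-variance of weight is ln(1 + 0.15^2) = 0.0223, and SE inflation = sqrt(sd^2 + 0.0223)/sd.

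| Log-SD of parameter | SE inflation |
|---|---|
| 0.3 | 1.117 |
| 0.4 | 1.067 |
| 0.6 | 1.030 |

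**4. Chance imbalance, same reading.** With 73 per arm (the evaluable target in Protocol 10.9; the secondary PK population may be smaller), the SE of the difference in mean log weight is sqrt(2 x 0.0223/73) = 0.025. The 95% range is 1.96 x 0.025, about ±5%. Weight CVs of 12% and 20% give about ±4% and ±6%. A 5% shift in the normalised ratio is therefore near the edge of what chance produces, not typical.

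**5. Bias.** A simulation of 20,000 trials with 73 per arm, weight CV 16% and parameter CV 40% (both assumed) used two-sided 5% t-tests on the log scale.

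| | Raw | Divided by weight |
|---|---|---|
| Rejection rate, true ratio 1.0 | 5.1% | 5.2% |
| Power, true ratio 0.80 | 93.7% | 89.8% |

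The normalised estimate of a true ratio of 0.80 averaged 0.80. Division by weight costs some power and causes no bias.

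**The case against.** The strongest reply is that little depends on this. The same sentence also t-tests the raw parameters, the endpoint is exploratory, and the AUC0-7d non-inferiority test in SAP 8.f is not described as dose-normalised. All of that stands and limits the point to the supplementary normalised versions.

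A reader might infer that the normalised t-tests end up comparing body weight between arms. The documents do not support that. Allocation is 1:1 and random, so the expected weight difference is zero; weight enters as noise and as chance imbalance. If dose means IU/kg, weight does not enter at all.

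A reader might also infer that dividing AUC0-7d by dose is an artefact. That needs two things the documents do not give: that dose means total IU, and that exposure at 20 IU/kg does not depend on weight. Protocol 2.4 says the PK of BPL HRIG has not been studied. If distribution volume does not scale with weight, dividing by total IU could be a fair adjustment.

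The shares in step 1 are open to challenge too. Protocol 2.3 describes HRIG studies that used duck-embryo vaccine, whereas this trial uses a chick-embryo cell vaccine (Protocol 2.8). The 86-89% rests on extrapolated decay and additivity. The undecayed 73% still leaves the peak mostly vaccine, so the conclusion for Cmax does not depend on the decay step.

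Finally, an IU/kg divisor will change little in a population that received the full dose. That is true, and is a reason not to expect much from normalising. It could matter more in the ITT version that both documents also call for, where a partial dose is possible.

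**Conclusion.** The point holds as a minor one. The dose-normalised Cmax, AUC0-t and AUC0-inf cannot be read as exposure per unit of HRIG, because the measured antibody is mostly vaccine response: 73% of the peak undecayed and 86-89% decayed on the Protocol 2.3 figures, with about 75-92% of AUC0-140 on rougher assumptions. Dividing the rate constant and half-life by dose has no justification under linear kinetics.

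The unit of dose must be stated. If it is total IU, the cost is an SE about 3-12% larger (assumed weight CV 15%, log-SD 0.6 to 0.3) and a chance shift of up to about 5% either way, with no bias on average. If it is IU/kg, the effect is close to nil. The raw t-tests and the AUC0-7d non-inferiority test are unaffected.

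**What to change.** In SAP 8.g and Protocol 10.5.4:

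- Delete the dose-normalised versions of Cmax, AUC0-t, AUC0-inf, the terminal rate constant and the half-life. Rely on the raw comparisons already planned, on the log scale where appropriate.
- If AUC0-7d is to be normalised, define the divisor as the IU/kg actually received: mL injected x potency of the injected lot / Day 0 weight. It then corrects only real departures from the planned IU/kg.

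Before that divisor is used, one conflict needs reconciling. Protocol 6.2 bases the comparator volume on the actual potency of BPL HRIG, while Protocol 6.1.2 and Appendix F refer to each product's own potency. This bears on what dose the comparator arm actually receives.

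The cost is wording only. Injected volume, lot number and Day 0 weight are already recorded, and potency is supplied per lot.
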